Appendix 2 Extension Phase B (revised per Amendment 04)

Extension B is only for subjects in Japan or countries where an EAP cannot be implemented, after having completed Extension A. (revised per Amendments 03 and 04)

Study Design and Plan

Extension B will consist of a Treatment Period and a Follow-up Period (up to 4 weeks). Treatment will continue as long as clinically appropriate according to the judgment of the investigator. In Japan, treatment of subjects in the Extension B will be completed when the subject reaches 12 years of age or when perampanel is commercially available in Japan for treatment of POS in pediatric subjects (4 to less than 12 years of age). In countries where an EAP cannot be implemented, participation in Extension B will continue as long as clinically appropriate according to the judgment of the investigator, until the subject reaches 12 years of age or perampanel oral suspension is commercially available. (revised per Amendment 04)

Subjects eligible for Extension B shall be subjects in Japan or in countries where an EAP cannot be implemented, after having completed Extension A of this study, are less than 12 years of age at the time of entering Extension B, and who in the opinion of the investigator continue to benefit from treatment with perampanel. (revised per Amendment 04)

Subjects will enter Extension B with their optimal perampanel dose (ie, the same dose of perampanel that they were maintained on at the end of Extension A). During the course of the Extension B, doses of perampanel and concomitant AEDs can be adjusted (concomitant AEDs can be used in accordance with the approved dosage and indication) based on clinical judgment.

In Japan, the maximum dose of perampanel is 12 mg/day. (revised per Amendment 04)

In countries where an EAP cannot be implemented, the maximum dose of perampanel is 12 mg/day in subjects not taking any concomitant EIAEDs, or 16 mg/day in subjects taking a concomitant EIAED. (revised per Amendment 04)

Tolerability at a minimum perampanel dose of 2 mg/day is required to continue in the program. Subjects who do not tolerate the minimum perampanel dose of 2 mg/day during the study will be discontinued from the study. (revised per Amendment 04)

Conversion to monotherapy on perampanel is also permitted at the discretion of the investigator, if it is considered appropriate to control the seizures.

The visit intervals in Extension B will be every 12 weeks. All visits to be done within ± 6 days of the schedule.

During Extension B, when a subject reaches 12 years of age, the subject would have to switch to the commercial perampanel product promptly, and an End of Study Visit should be conducted. If the subject does not switch to the commercial perampanel product promptly, study drug treatment will be discontinued. A Discontinuation Visit should be conducted, and a Follow-up Visit should be conducted 4 weeks (± 7 days) later. (revised per Amendment 03)

In Japan, when perampanel is commercially available for treatment of POS in pediatric subjects (4 to less than 12 years of age), all subjects will have to switch to perampanel commercial product promptly, and an End of Study Visit should be conducted. If the subject does not switch to commercial product promptly, study drug treatment will be discontinued. A Discontinuation Visit should be conducted for that subject, and a Follow-up Visit should be conducted 4 weeks (± 7 days) later. (revised per Amendments 03 and 04)

In countries where an EAP cannot be implemented, participation in Extension B will continue as long as clinically appropriate according to the judgment of the investigator, until the subject reaches 12 years of age or perampanel oral suspension is commercially available. (revised per Amendment 04)

The investigator may discontinue the subject from the study at any time for safety or administrative reasons. When the decision is made to discontinue to subject from the study, a Discontinuation Visit and a Follow-up Visit 4 weeks (± 7 days) later should be conducted for that subject. (revised per Amendment 03)

Subjects who discontinue or choose not to switch to the commercial product, once perampanel is commercially available will require a Follow-up Visit which will be conducted 4 weeks (± 7 days) after the Discontinuation Visit. (revised per Amendment 04)

Subjects who switch to the commercial product, once perampanel is commercially available will require an End of Study Visit. A Follow-up Visit will not be required for subjects who switched to the commercial product and attended an End of Study Visit. (revised per Amendment 04)

The sponsor reserves the right to terminate the program at any time.

Study Drug Supplies

Perampanel will be supplied as 0.5 mg/mL oral suspension.

Schedule of Procedures/Assessments

Table 6 presents the Schedule of Procedures/Assessments for the Extension B. During Extension B, laboratory tests will be performed by the local laboratory.

Assessments

Safety Assessments

Safety will be assessed by monitoring of AEs, withdrawal from treatment, clinical laboratory tests, vital signs, and weight.

Other Assessments

Concomitant medication usage will be monitored.

Statistical Analyses

Analysis Sets

Safety Analysis Set is the group of subjects who received at least 1 dose of study drug and had at least 1 postdose safety assessment in Extension B.

Safety Analyses

All safety analyses will be performed on the Safety Analysis Set. Safety data that will be evaluated include TEAEs, clinical laboratory parameters and vital signs.

Adverse Events

The AE verbatim descriptions (investigator terms from the CRF) will be classified into standardized medical terminology using MedDRA. Adverse events will be coded to the MedDRA (version 18.1 or higher) lower level term closest to the verbatim term. The linked MedDRA PT and primary SOC are also captured in the database.

A TEAE is defined as an AE that emerges during treatment, having been absent at pretreatment (Baseline) or

- Re-emerges during treatment, having been present at pretreatment (Baseline) but stopped before treatment, or
- Worsens in severity during treatment relative to the pretreatment state, when the AE is continuous.

Only those AEs that are treatment-emergent will be included in summary tables. All AEs, treatment-emergent or otherwise, will be presented in subject data listings.

Adverse events will be summarized using the Safety Analysis Set. The incidence of TEAEs will be reported as the number (percentage) of subjects with TEAEs by SOC and PT. A subject will be counted only once within an SOC and PT, even if the subject experienced more than 1 TEAE within a specific SOC and PT. The number (percentage) of subjects with TEAEs will also be summarized by relationship to study drug (related or not related).

The number (percentage) of subjects with treatment-related TEAEs will be summarized by SOC and PT. Treatment-related TEAEs include those events considered by the investigator to be related to study treatment.

Laboratory Values

Laboratory results will be summarized using SI units, as appropriate. For all quantitative parameters listed in [Section 9.5.1.5.3](#), the actual value and the change from baseline to each postbaseline visit and to the end of treatment (defined as the last on treatment value) will be summarized by visit using descriptive statistics. Percentages will be based on the number of subjects with both nonmissing baseline and relevant postbaseline results.

Vital Signs

Descriptive statistics for vital signs parameters (ie, systolic and diastolic BP, pulse, respiratory rate, temperature, weight) and changes from baseline will be presented by visit.

Table 6 Schedule of Procedures/Assessments in Study E2007-G000-311: Extension B (revised per Amendments 03 and 04)

Phase	Extension					
	Treatment					
Period						
Visit/Timing	At Initial Assessment ^a (Day 1, Week 1)	Scheduled Visit ^b (Every 12 weeks)	Unscheduled Visit ^c	End of Study	Discontinuation Visit ^d	Follow-Up ^e (4 Weeks After Discontinuation Visit)
Procedures/Assessments						
Review risk/benefit of continued therapy with perampanel and verify age eligibility	X	X	X			
Concomitant medications and Concomitant AED(s)	X ^f	X	X	X	X	X
Study drug compliance	X ^f	X	X	X	X	
Vital signs	X ^f	X	X	X	X	X
Weight	X ^f	X	X ^g	X	X	X
Clinical laboratory evaluations	X ^f	X	X ^g	X	X	X
Urine pregnancy test ^h	X ^f	X	X ^g	X	X	X
Dispense study drug	X	X	X ⁱ			
Retrieve unused study drug		X	X ⁱ	X	X	
Adverse events	X ^f	X	X	X	X	X

AED = antiepileptic drug, POS = partial-onset seizures.

- a: Perform on the final visit of Extension A Maintenance Period (ie, Visit 12).
- b: Visit window ±6 days.
- c: At the unscheduled visit, selected assessments will be performed based on investigator’s judgment of subject’s condition.
- d: Once a subject reaches 12 years of age or perampanel is commercially available, the subject would have to switch to the commercial product promptly. If a subject does not switch to the commercial product promptly, a Discontinuation Visit and a Follow-up Visit 4 weeks (±7 days) later should be conducted for the subject.
- e: Follow-up Visit is not required for subjects who will be switching to the commercial product and attend an End of Study Visit.

Table 6 Schedule of Procedures/Assessments in Study E2007-G000-311: Extension B (revised per Amendments 03 and 04)

Phase	Extension					
Period	Treatment					
Visit/Timing	At Initial Assessment ^a (Day 1, Week 1)	Scheduled Visit ^b (Every 12 weeks)	Unscheduled Visit ^c	End of Study	Discontinuation Visit ^d	Follow-Up ^e (4 Weeks After Discontinuation Visit)

f: Refer to the data recorded during the final visit of Extension A Maintenance Period (ie, Visit 12).

g: At the discretion of the investigator.

h: Female subjects age 8 years old and above, or of childbearing potential, only.

i: Dispense study drug or Retrieve unused study drug should be done, if necessary.

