Safety analyses will be performed similarly to the Core Study analyses and all analyses will be on the perampanel treatment duration (Core Study and Extension A). (revised per Amendment 03) The incidence of TEAEs, SAEs, AEs associated with fatal outcomes or leading to discontinuations, and AEs leading to dose adjustment will be summarized. Laboratory parameters, vital signs, and ECG parameters will be summarized. Change from baseline in CBCL, ABNAS, and LGPT, change from baseline in growth parameters, change from baseline in EEG parameters, the frequency of EEG abnormalities, and the proportion of subjects with any treatment-emergent report of suicidal ideation and behavior and intensity of these behaviors, will also be summarized descriptively. Baseline for these parameters is the last non-missing value before the 1st perampanel dose.

Extension B

Safety analyses for Extension B are described in [Appendix 2](#). (revised per Amendments 03 and 04)

Exploratory Analyses

The change from baseline in EQ-5D-Y at Week 23 and Week 52 will be summarized.

Interim Analyses

An independent data monitoring committee (DMC) will be constructed to monitor the safety data. The responsibilities, membership, and purpose of the DMC, the timing of the meeting(s), and an outline of the plan for review of the safety data will be documented in the DMC Charter.

Analyses for regional submissions may be performed during the course of the study. (revised per Amendment 02)

Sample Size Rationale

A sample size of at least 160 subjects (with up to 40 subjects with PGTC and the balance with POS), is deemed sufficient for safety evaluation in this age group (age 4 to <12 years). (revised per Amendment 02) This sample size matches the total number of adolescents who were enrolled in the 4 global Phase 3 efficacy and safety studies that support the POS and PGTC indications.

For purposes of registration in Japan, it has been determined that a sample size of 65 subjects enrolled in Japan will provide 80% power to exclude the possibility that there would be a reduction smaller than that observed in the placebo arm of Study E2007-J000-335 (ie, 10.5%).

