9 INVESTIGATIONAL PLAN

9.1 Overall Study Design and Plan

This is a multicenter, open-label single-arm study in children (ages 4 to <12 years) with inadequately controlled POS or PGTC. The study will consist of a Core Study and Extension Phase (Extension A, for all countries in the study) with Extension Phase (Extension B) available for subjects enrolled in Japan and in countries where an EAP cannot be implemented, after having completed Extension A. (revised per Amendments 03 and 04) Subjects will be stratified by age (≥ 4 to <7 years, 7 to <12 years) with at least 30% of subjects enrolled in the equal or greater than 4 to less than 7 year age group for each seizure type (ie, at least 36 with POS and at least 12 with PGTC).

Core Study

The Core Study will consist of the following 2 phases: Pretreatment and Treatment Phase.

The Pretreatment Phase will consist of a Screening/Baseline Period that lasts up to 4 weeks ± 3 days outside of Japan. Subjects in Japan are required to complete 4 full weeks ± 3 days of the Screening/Baseline Period. However, subjects outside of Japan may begin treatment as soon as baseline procedures have been completed and documentation of eligibility (such as a documented seizure diary entry for a qualifying seizure during the preceding 12 weeks prior to Visit 2 or a qualifying seizure during the prospective Screening/Baseline Period) has been established. (revised per Amendment 02) During this phase, subjects will be assessed for eligibility to participate in the study. Efforts should be made to perform all clinical laboratory and screening tests on the scheduled day of Visit 1, or as close as possible to that day, within the 4 week period prior to Visit 2. (revised per Amendment 01)

The Treatment Phase will consist of 3 periods: Titration (up to 11 weeks), Maintenance (up to 12 weeks), and Follow-up (up to 4 weeks; only for those subjects not rolling over into Extension A). (revised per Amendments 01, 02, and 03)

Extension A

Extension A will consist of a Maintenance Period (up to 29 weeks) and a Follow-up Period (up to 4 weeks; only for those subjects not entering into Extension B). (revised per Amendments 02, 03, and 04)

An overview of the study design is presented in [Figure 1](#).

Extension B

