9.5.1.5.3 LABORATORY MEASUREMENTS

Clinical laboratory tests to be performed, including hematology, chemistry, and urinalysis, are summarized in [Table 3](#). Subjects should be in a seated or supine position during blood collection. The Schedule of Procedures/Assessments ([Table 4](#)) shows the visits and time points at which blood for clinical laboratory tests and urine for urinalysis will be collected in the study (Core Study).

Table 3 Clinical Laboratory Tests

Category	Parameters
Hematology	Hematocrit, hemoglobin, platelets, RBC count, and WBC count with differential (basophils, eosinophils, lymphocytes, monocytes, neutrophils) (revised per Amendment 01)
Chemistry	
Electrolytes	Chloride, potassium, sodium
Liver function tests	Alanine aminotransferase, alkaline phosphatase, aspartate aminotransferase, gamma glutamyl transpeptidase, direct bilirubin, total bilirubin
Renal function tests	Blood urea/blood urea nitrogen, creatinine
Other	Albumin, calcium, cholesterol, globulin, glucose ^a , lactate dehydrogenase, phosphorus, total protein, triglycerides ^a , uric acid
Urinalysis	Bacteria, casts, crystals, epithelial cells, glucose, ketones, occult blood, pH, protein, RBCs, specific gravity, WBCs, Urine drug screen ^b (revised per Amendment 01)

RBC = red blood cell, WBC = white blood cell.

- a: Fasting samples to be taken at baseline and at end of treatment or early discontinuation, with fasting window (interval) between 2 and 4 hours.
- b: To be performed only at baseline. (revised per Amendment 01)

Clinical laboratory tests during the Core Study and Extension A will be performed by a central laboratory. (revised per Amendment 03) All blood and urine samples will be collected and sent to the central laboratory on the day of collection unless otherwise instructed. In cases of a safety concern, blood samples will be split (or 2 samples drawn) to allow a local laboratory analysis in addition to the central laboratory.

A laboratory abnormality may meet the criteria to qualify as an AE as described in this protocol (see [Section 9.5.1.5.1](#) and the CRF Completion Guidelines). In these instances, the AE corresponding to the laboratory abnormality will be recorded on the AE CRF.

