9.7.1.8.3 LABORATORY VALUES

Laboratory results will be summarized using Système International (SI) units, as appropriate. For all quantitative parameters listed in [Section 9.5.1.5.3](#), the actual value and the change from baseline to each postbaseline visit and to the end of treatment (defined as the last on-treatment value) will be summarized by visit using descriptive statistics. Percentages will be based on the number of subjects with both nonmissing baseline and relevant postbaseline results.

Laboratory test results will be assigned a low/normal/high (LNH) classification according to whether the value was below (L), within (N), or above (H) the laboratory parameter's reference range. For each laboratory parameter, shift from baseline (LNH) to each postbaseline visit and at the end of treatment will be presented. Similar shift tables from baseline (LNH) to the highest/lowest postbaseline value will also be presented.

[Appendix 3](#) (Sponsor's Grading for Laboratory Values) presents the criteria that will be used to identify subjects with treatment-emergent markedly abnormal laboratory values (TEMAV). Except for phosphate, a TEMAV was defined as a postbaseline value with an increase from baseline to a grade of 2 or higher. For phosphate, a TEMAV was defined as a postbaseline value with an increase from baseline to a grade of 3 or higher. The number and percentage of subjects with TEMAVs will be presented; each subject will be counted once in the laboratory parameter high and low categories, as applicable. Markedly abnormal laboratory values will be flagged in the subject data listings.

For ALT and AST analysis, the number of subjects with greater than 3 times, but less than 5 times the ULN and the number of subjects with greater than 5 times the ULN will be summarized. For bilirubin, a summary of the number of subjects with serum concentrations greater than 2 times the ULN will be created.

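### Extension B laboratory changes subtract a central-laboratory baseline from a local-laboratory result, so laboratory offsets cannot be separated from drug or time effects in that table

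*Protocol*

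**What the plan says.** Protocol 9.5.1.5.3 sets the laboratory for the first two phases: "Clinical laboratory tests during the Core Study and Extension A will be performed by a central laboratory". Appendix 2 changes it for the third: "During Extension B, laboratory tests will be performed by the local laboratory".

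For the Extension B initial assessment, Table 6 note f takes the laboratory values from the end of Extension A: "Refer to the data recorded during the final visit of Extension A Maintenance Period (ie, Visit 12"). Under Laboratory Values, Appendix 2 plans descriptive statistics by visit of "the actual value and the change from baseline to each postbaseline visit and to the end of treatment". The only standardisation it names is units: "Laboratory results will be summarized using SI units, as appropriate". It does not say which baseline is meant. The other candidate appears in the Synopsis under Extension A: "Baseline for these parameters is the last non-missing value before the 1st perampanel dose". Section 8.2.1 of the Extension SAP uses the same rule.

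The Core Study plan is richer. Protocol 9.7.1.8.3 adds range-based displays ("shift from baseline (LNH) to each postbaseline visit and at the end of treatment will be presented"), graded markedly abnormal values, and counts of ALT, AST and bilirubin by multiple of ULN. Appendix 1 repeats these for Extension A. Appendix 2 contains none of them.

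**The concern.** A change from baseline is interpretable when both measurements come from the same assay, or when each is scaled to its own laboratory's range. In Extension B every laboratory change is a local result minus a central one. The switch of laboratory coincides with entry to Extension B, and Protocol 9.1 leaves no concurrent control: "This is a multicenter, open-label single-arm study in children". Nothing in the planned table can distinguish an assay offset from a drug effect, growth, or the concomitant-AED changes that Extension B permits.

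The range-based displays, which are less exposed to a change of laboratory, are dropped in the one phase where the laboratory changes. This is also potentially the longest exposure. Participation can run to age 12, so a child enrolled at 4 who has had 52 weeks of treatment could in principle stay about 12 − 4 − 1 = 7 years, if perampanel does not become commercially available first. Laboratory tests are among the few safety assessments kept, and are collected every 12 weeks.

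**Working it through.** The plan states no figure on this point, so there is none to reproduce. The check traces the source of each number and then illustrates size under labelled assumptions.

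**Source of each term**

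- Extension B visit value: local laboratory (Appendix 2).
- Baseline candidate 1, Visit 12 of Extension A (Table 6 note f): central laboratory (9.5.1.5.3).
- Baseline candidate 2, last value before the first dose (Synopsis; Extension SAP 8.2.1): Core Study pretreatment, central laboratory.

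The central baseline is an inference, because Appendix 2 names neither candidate. It is safe because both lead to the same place. No paired central/local sample or local baseline is planned; 9.5.1.5.3 allows a parallel local analysis only when there is a safety concern.

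**Other documents.** The Core SAP is confined to the Core Study. The Extension SAP's visit windows end at Week 52, its reference list cites protocol v5.0 (Extension B was added in v7.0), and apart from notes to its design figure it does not deal with Extension B.

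**Form of the error.** Write T0 and T1 for the true values at baseline and follow-up, and b for the local laboratory's proportional offset from the central one. Then

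raw change = T1(1 + b) − T0 = (T1 − T0) + b × T1.

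The first term holds drug, growth, time and co-medication effects; the second is purely assay. SI conversion rescales units and leaves b untouched.

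**Size under assumed offsets, true change zero, baseline mean set to 100**

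- Common offset of −10%, −5%, +5% or +10%: mean raw change of −10, −5, +5 or +10. More subjects do not reduce it.
- Independent offsets with SD s over k equally sized laboratories: the SD of the mean spurious change is s/√k, and the 95% range is ±1.96 × s/√k.
  - s = 5%: ±4.38 for k = 5, ±2.19 for k = 20.
  - s = 10%: ±8.77 for k = 5, ±4.38 for k = 20.

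**The same on an ALT scale.** All inputs are assumed: mean 20 U/L, SD of change 8 U/L, 50 children. SE = 8/√50 = 1.13 U/L.

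- Common offset of 10% to 20%: 2 to 4 U/L, or 2/1.13 = 1.8 to 4/1.13 = 3.5 SE.
- Independent offsets: ±2.19%, ±4.38% and ±8.77% of 20 are ±0.44, ±0.88 and ±1.75 U/L, or about 0.4, 0.8 and 1.6 SE.

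The answer therefore depends heavily on whether local laboratories err in the same direction. The SE is only a yardstick, since Appendix 2 plans no test.

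**What range scaling does.** Take a child at 0.8 × ULN throughout, with a central ULN of 40 (value 32). At local ULNs of 30, 35 and 45 the local values are 24, 28 and 36, so the raw changes are −8, −4 and +4. The change in multiples of ULN is zero each time. This assumes that the laboratories' difference is fully reflected in their ranges.

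**What Appendix 3 grades do.** Of its 24 rows, 6 are multiples of ULN: alkaline phosphatase, ALT, AST, bilirubin, creatinine and GGT. Almost all of the other 18 reach the counted grades at fixed concentrations, for example haemoglobin below 10.0 g/dL or potassium above 5.5 mmol/L. An assay offset moves those counts just as it moves raw values.

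**The case against.** The strongest reply is about proportion. The amendment log gives managed access as the reason for Extension B. It is limited to Japan and countries without an extended access program, has no efficacy analysis set and a reduced assessment schedule, and the study's endpoints with a stated horizon stop at Week 52. Local testing in such a phase is a defensible operational choice, and a single-arm design could not attribute changes to drug anyway. All of this stands. It limits the weight of the point, but it does not make the raw change interpretable.

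Three stronger readings are tempting, and the documents do not support them:

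- A reader might infer that Extension B has no count of laboratory abnormalities. Protocol 9.5.1.5.1 makes an abnormality that leads to intervention, or to withholding or withdrawal of drug, an adverse event, and Appendix 2 counts TEAEs by SOC and PT. What is missing is a range-based count.
- A reader might infer that a real trend would be hidden. Actual values are also summarised by visit. If a child stays with one local laboratory, the offset is a single step at the first local visit, and later visits compare like with like.
- A reader might infer that an effect of 2 to 3.5 standard errors should be expected. That needs every local laboratory to be biased 10% to 20% in the same direction; independent offsets give about 0.4 to 1.6.

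It is also fair that a low/normal/high shift from Visit 12 compares classifications under two sets of reference ranges. Range scaling reduces the problem without removing it.

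**Conclusion.** The point holds as a limited one. Followed as written, Appendix 2 produces change-from-baseline figures in which between-laboratory offset can appear as, and cannot be separated from, drug or time effect. This rests on the inference that the baseline is a central value, which is true of both candidates. The size cannot be determined from the documents; every offset, SD, laboratory count and sample size used above is an assumption.

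Only the descriptive Extension B laboratory table is affected. The Core Study primary safety analysis, the Extension A laboratory analyses and the Japan efficacy criterion are untouched. A reader might go further and say that assay differences will be reported as drug effects; the documents do not establish that any offset exists, only that the plan could not recognise one. This is a worthwhile, inexpensive improvement rather than a threat to the study's conclusions.

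**What to change.** In Appendix 2, and in whichever analysis plan covers Extension B:

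1. State the laboratory baseline for Extension B.
2. Record each local laboratory's reference ranges in the database.
3. Add low/normal/high shifts, each result classified by the reporting laboratory's own range.
4. Add multiples of ULN for ALT, AST, bilirubin, alkaline phosphatase and creatinine.
5. Keep the by-visit actual values, and label any raw change from Visit 12 or earlier as crossing laboratories.
6. Optionally, add change from the first local value as a secondary reference. It stays within one assay if the child keeps the same laboratory, but it describes only change after that visit.

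Appendix 3 grades should not be presented as range-scaled, for the reason given in the row count above. Moving raw values to listings alone is not advised, because it would discard a local series that is comparable within a laboratory.

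The cost is appendix and SAP wording plus modest data-management work to collect local ranges. No extra visit or blood draw is needed.
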